5 CHIVITT OBJECTIVES

Table: Objectives and Endpoints (Outcome Measures)

Objectives	Endpoints (Outcome Measures)
Primary	

 • To determine the relative contribution of the various modes of transmission 	
 • SAR of influenza infection will be determined through virological confirmation, symptomatic infection, or serological evidence
Secondary	

 • To measure influenza viral parameters in Donors and Recipients • To measure influenza illness parameters in Donors and Recipients to assess the impact of aerosol exposure to influenza on disease severity • To evaluate the role of serologic antibody levels on influenza transmission, susceptibility, and immunologic response to infection 	
 • Incidence, duration, and quantity of virus shedding in donors and recipients • Disease severity parameters in donors and recipients • HAI, NI, and FRNT titers, HA/NA anti-stalk ELISA, and ADCC reporter assays. • Measurement and modeling of aerosol size, virus number per aerosol particle,

• To estimate the infective dose of influenza virus	deposition and environmental dispersion characteristics, and rate of shedding
Exploratory	

 To evaluate the role of mucosal antibody and cellular immunity in transmission and susceptibility. To characterize the quantum of airborne influenza infection and extend models of aerosol inhalation risk from well-mixed to non-well mixed conditions and the personal breathing zone. 	
 Potential assays include IgA in nasal secretions and collection and analysis of cellular immune markers. Exhaled breath viral loads and ambient viral concentrations, environmental parameters, video analysis of individual movement and interpersonal proximity and behaviors.

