8.2 Research Laboratory Evaluations

HAI and FRNT Assays

The ability of antibodies to inhibit the interaction of hemagglutinin (HA) protein on the surface of influenza virus with sialic acids on the surface of red blood cells (RBCs) will be examined by hemagglutinin inhibition (HAI) assay performed on serum samples from study participants at the specified collection timepoints. The readout will be the ability of antibodies to inhibit hemagglutination, HAI titers. For H3N2 viruses that have no HA activity, serum antibody will be titred using a focus reduction neutralization test (FRNT) in which the ability of the serum to inhibit the formation of infectious foci in cell culture will be measured. The HAI and FRNT assays are to be performed with deidentified specimens at a collaborating lab ([name], Icahn School of Medicine at Mount Sinai, New York, NY). The virus strain-specific HAI or FRNT titer will be considered the primary method for determining a participant's immunity.

Potential Antibody Assays if funding is available

A brief listing of some of the potential additional antibody assays which may be performed on serum and/or nasal wash specimen includes the following:

- Microneutralization (MN) assay, measures the ability of antibodies to prevent cytopathologic effects in cell cultures infected with influenza viruses.
- Neuraminidase inhibition (NI) assay, measure antibodies that block the enzymatic activity of the neuraminidase protein (NA), a surface glycoprotein which cleaves sialic acid residues.
- Enzyme-linked immunosorbent assay (ELISA), measures binding antibodies against full-length HA, HA-stalk, NA, and other influenza antigens.

- Influenza virus protein microarray, an approach which can measure the “landscape” of serum antibodies by measuring the binding against hundreds of HA and NA proteins simultaneously and spanning multiple virus subtypes and strains.
- Antibody-dependent cellular cytotoxicity (ADCC) assay, functional antibody assay.

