9 OUTCOMES AND DATA ANALYSIS

9.1 Primary Outcome Measure – Attack Rate of Influenza

The SAR of influenza infection will consist of virological confirmation, symptomatic infection, or serological evidence of an influenza infection.

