9.1.3 Serological Confirmation of Influenza Infection

Seroconversion. A positive seroconversion will be defined as achieving ≥ 4 -fold increase in serum HAI titer from baseline. The serological assessment will be performed in batched analyses and will not be available for day-to-day decisions.

Seropositive. A seropositive will be defined as a serum HAI titer of ≥ 40 at 1-month post-CHIVITT. The serological assessment will be performed in batched analyses and will not be available for day-to-day decisions.

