9.3 Analysis Plan

We will plan to analyze the binary outcome (SAR of influenza infection) using a generalized estimating equation (GEE) with a logistic link function. Individuals sharing a CHIVITT cohort will be considered as a cluster and the dependence will be adjusted by the working correlation in the GEE model. The effect of the interventions will be treated as independent, and the analysis will be controlled for sex, race-ethnicity, and age \geq or < 30 years. We will examine sex as a biological variable for a main effect on infection risk but will not have sufficient power to perform subgroup analysis. R markdown and reproducible statistical analysis will be applied to ensure maximal reproducibility of the data analysis.

Continuous data will be transformed (e.g., Box-Cox transformation) to meet the normality assumption in the analysis. To compare proportions among unpaired samples, we will use logistic regression and adjust covariates as needed. For paired samples, we will use the conditional logistic regression. To examine the group effect on the continuous effect, we will use the general linear model. To test for a trend across

groups, we will use the chi-squared test for trend to compare proportions or Cuzick's test for trend to compare continuous data. Spearman correlation tests will be used to assess correlations between non-binary ordinal variables. The association of immunological measures and other covariates on the risk of infection will be examined using generalized estimating equations (GEE) with a Poisson distribution and robust standard errors to overcome the potential overdispersion. Principal components analysis (PCA) will be used to assess the extent to which variables can be summarized using a smaller number of components. The potential effects of age and sex will be examined in all multivariable models.

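### Section 9.3 relates antibody titre to infection risk although HAI titre also helps define infection; the 1-month HAI of 40 rule can mask or reverse protection if some Recipients enter at or near 40

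*Protocol*

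**What the plan says.** **The model.** Protocol 9.3 states: "The association of immunological measures and other covariates on the risk of infection will be examined". The method is a GEE with a Poisson distribution and robust standard errors. The section gives no separate case definition for this model and names no time point for the immunological measures.

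**The outcome.** Section 9.1 states: "The SAR of influenza infection will consist of virological confirmation, symptomatic infection, or serological evidence of an influenza infection". Section 9.1.3 gives two serological rules, both in HAI. Seroconversion is at least a "4 -fold increase in serum HAI titer from baseline". For the other, "A seropositive will be defined as a serum HAI titer of" 40 or more at one month, with no rise required.

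**The predictor.** A secondary objective in section 5 is "To evaluate the role of serologic antibody levels on influenza transmission, susceptibility, and immunologic response to infection", and HAI comes first among its listed endpoints. In section 8.2, "The virus strain-specific HAI or FRNT titer will be considered the primary method" for establishing a participant's immunity.

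**Entry titres.** Section 6 makes low titre only part of the basis for selecting Recipients, and the titre may be up to a year old. Section 4.1 sets no titre limit. Section 8.1.1 draws serum at admission for HAI and FRNT.

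**The concern.** Baseline HAI sits on both sides of the model. It is the denominator of the fold rise. In anyone who is not infected, it also largely decides whether the 1-month titre reaches 40. An uninfected Recipient who enters at 40 and stays there is scored as infected, and such people are by construction at the top of the titre scale. The regression then reads high titre as high risk.

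The secondary objective on antibody and susceptibility depends on this analysis. The distortion is a bias in the outcome definition, so a larger sample would not remove it.

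**Working it through.** The plan states no figure for this analysis, so there is none to reproduce. The check asks what ratio per titre doubling the plan's outcome returns when the true ratio is known.

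**Inputs from the Protocol**
- Attack rate of 25% (9.2), applied here as the average over the titre mix.
- The two HAI rules: at least a 4-fold rise, or at least 40 at one month (9.1.3).

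**Assumptions, because the Protocol gives no figures**
- Entry titres of 5, 10, 20 and 40 in the mixes shown below.
- Assay error SD of 0.3 to 0.7 log2, with readings rounded to two-fold dilutions.
- Virological sensitivity of 90%.
- Mean rise after infection of 3 log2 (SD 1).
- The symptomatic leg of the composite is not modelled.

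**By hand, no assay error, 10% at 40.** The mix is 50/25/15/10% and the true ratio is 0.70.
- Risk at titre 5: 0.25 / (0.50 + 0.25×0.70 + 0.15×0.49 + 0.10×0.343) = 0.25 / 0.7828 = 0.319.
- True risks at 5, 10, 20 and 40: 0.319, 0.224, 0.156 and 0.110.
- Under the 40 rule everyone at 40 is a case, so the last figure becomes 1.00.
- If every infection is found, the attack rate becomes 0.50×0.319 + 0.25×0.224 + 0.15×0.156 + 0.10×1.00 = 0.339, against a true 0.25. The highest-titre group now has the highest apparent risk.

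**Simulation with assay error.** Poisson regression on measured baseline log2 titre, 300,000 Recipients per setting, true ratio 0.70. Each cell gives the ratio per doubling at error SD 0.3 / 0.5 / 0.7.

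| Entry titres 5/10/20/40 (%) | Virology, 4-fold rise or HAI ≥40 | Virology or 4-fold rise | Virology only |
|---|---|---|---|
| 50/25/15/10 | 1.32 / 1.26 / 1.20 | 0.71 / 0.75 / 0.77 | 0.71 / 0.75 / 0.77 |
| 50/30/18/2 | 0.98 / 1.04 / 1.03 | 0.72 / 0.76 / 0.76 | 0.72 / 0.77 / 0.79 |
| 50/30/20/0 | 0.78 / 0.92 / 0.96 | 0.72 / 0.75 / 0.76 | 0.72 / 0.76 / 0.80 |
| 60/40/0/0 | 0.75 / 0.79 / 0.81 | 0.75 / 0.79 / 0.79 | 0.76 / 0.83 / 0.87 |

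Virology alone departs from 0.70 only through ordinary attenuation by assay error. In the last row the 40 rule adds at most 0.02 to the middle column.

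**No true antibody effect (true ratio 1.00).** The three-part outcome gives 1.30 to 1.49 with 10% at 40, 1.17 to 1.22 with 2%, and 1.06 to 1.12 with none at 40 but 20% at 20. Virology or 4-fold rise gives 0.90 to 1.00 across all four mixes, a small bias the other way. Virology alone gives 0.99 to 1.01.

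**A different error model.** Here risk is 25% at the lowest titre, one-dilution error occurs in 0% or 10% of readings in each direction, and 80% of the infected mount a rise. The three-part outcome gives 1.52 and 1.43 with 10% at 40 (mix 40/30/20/10). It gives 0.71 and 0.90 with none at 40 (mix 45/30/25/0).

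**The case against.** **The harm belongs to the seropositive rule.** This stands for the most part. With that rule removed and the 4-fold rule kept, the ratio stays at 0.71 to 0.79 against a true 0.70. A reader might infer that any outcome containing a fold rise hides or reverses protection. The table does not support that.

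**Recipients are chosen for low titres, so 10% at 40 is invented.** It is an assumption. However, low titre is only part of the selection basis, the titre may be a year old, and 4.1 has no cut-off. Even 2% at 40 is enough to erase a ratio of 0.70. If all enter at 10 or below, the concern has no practical weight.

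**The case definition and time point are matters for the SAP.** The sentence in 9.3 does not name HAI or the composite, and 9.1.1 calls the BioFire panel the primary means of determining infection, so a virological reading is possible. But 9.1 defines infection as the composite, and 9.3 offers no other definition. A SAP that followed the Protocol faithfully would carry the bias.

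**The overlap does not reach every measure.** Correct. For H3N2 viruses without HA activity, section 8.2 uses FRNT while 9.1.3 stays in HAI. For FRNT, NI, ELISA and ADCC the link is indirect, through correlation with HAI, and its size was not calculated.

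**Virology has its own weakness.** If antibody lowers shedding, detection depends on titre. With sensitivity falling 10% per doubling and no true effect, virology alone gives 0.90 to 0.92. Section 6.9 also allows discharge 2 days after the last exposure and recognises late infections, which serology could catch. Both are reasons to keep a sensitivity analysis. Neither is a reason to keep the absolute rule.

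**Conclusion.** The concern holds for HAI and measures strongly correlated with it. As written, the predictor is part of the outcome, and the absolute 1-month rule does most of the damage.

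For a true ratio of 0.70 at a 25% attack rate, the result depends on how many Recipients enter at or near 40. Protection is reversed with 10% at 40, erased with 2%, and attenuated with none at 40 but 20% at 20. The 40 rule does nothing material if all enter at 10 or below. These sizes rest on assumed titre mixes and an assumed error SD of 0.3 to 0.7 log2.

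A reader might infer that the antibody result will certainly have the wrong sign, or that every immunological measure is affected alike. The Protocol supports neither. It does not exclude entry at 40, but it does not show that such entries will occur.

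The point concerns a secondary objective. The change is worth making because it is cheap and the error could present a protective antibody as irrelevant or harmful.

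**What to change.** Add to 9.3: for the GEE of immunological measures on infection risk, the outcome is virologically confirmed infection under 9.1.1, and the predictor is the admission (pre-exposure) titre. Report the composite, without the rule of HAI 40 or more with no rise, as a sensitivity analysis.

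No new data are needed. Admission serum (8.1.1) and daily respiratory sampling (8.1.3) are already planned, and the primary attack-rate analysis is unchanged.

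The cost is that serology-only and symptomatic-only cases no longer count as events in this secondary model. Virological detection may itself depend somewhat on titre. The sensitivity analysis would show the direction of that: in the setting above, virology or 4-fold rise gives 0.95 to 0.99 against 0.90 to 0.92 for virology alone. It cannot measure it precisely, since 175 Recipients at 25% yield at most about 44 infections (175 × 0.25 = 43.75).

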10 OPERATIONAL CONSIDERATIONS

10.1 Regulatory, Ethical, and Study Oversight Considerations

This study will be conducted in accordance with the ethical principles set out in the World Medical Association Declaration of Helsinki, The Council for International Organizations of Medical Sciences (CIOMS) International Ethical Guidelines for Biomedical Research Involving Human Subjects, and in conformity with ICH GCP regulations.

This study will be conducted under the auspices of the University of Maryland, Baltimore Institutional Review Board (UMB IRB), Baltimore, Maryland, U.S.A. (DHHS OHRP Federal Wide Assurance number 00007145).

When additional sites are added for the recruitment of Donors, the respective IRB must also provide review and approval of the study prior to the recruitment of participants. In instances where a Reliance Agreement can be negotiated, the UMB IRB will maintain oversight of the study.

The principal investigator will obtain IRB approval for this protocol and send supporting documentation to the DMID before initiating recruitment of subjects. The IRB must be registered with OHRP as applicable to the research. DMID must receive the documentation that verifies IRB-approval for this protocol, associated informed consent documents, and upon request any recruitment material and handouts or surveys intended for the subjects, prior to the recruitment and enrollment of subjects. Any amendments to the protocol or consent materials will be approved by the IRB before they are implemented. IRB review and approval will occur at least annually throughout the enrollment and follow-up of subjects and may cease if annual review is no longer required by applicable regulations and the IRB. The investigator will notify the IRB of deviations from the protocol and reportable new information, as applicable to the IRB policy.

10.2 Informed Consent Process

Informed consent is a process that is initiated prior to the individual agreeing to participate in the study and continues throughout the subject's participation in the study. Before any study-related activities and in agreement with ICH-GCP and the applicable local ethical and regulatory requirements, the site investigator must ensure that the subject is fully informed about the objectives, procedures, potential risks, and potential benefits of study participation. Subjects will receive a concise and focused presentation of key information about the study, verbally and with a written or electronic consent form. The explanation will be organized and presented in lay terminology and language that facilitates understanding why one might or might not want to participate. Additional screening activities may occur by phone using an IRB approved process that ensures confidentiality. The key information about the purpose of the study, the procedures and experimental aspects of the study, risks and discomforts, any

expected benefits to the subject, and alternative treatment will be presented first to the subject. The subject will be asked to consent for future use of specimens for secondary research; the subject will be instructed to submit a written request for stored specimens to be destroyed. Information will also include the foreseeable circumstances and/or reasons under which the subject's participation in the trial may be terminated. The subjects will be informed that participation is voluntary and that they are free to withdraw from the study for any reason at any time without penalty or loss of benefits to which the subject is otherwise entitled. The rights and welfare of the subject(s) will be protected by emphasizing to them that the quality of their medical care will not be adversely affected if they decline to participate in this study.

Subjects will be informed that records identifying the subject will be kept confidential, and, to the extent permitted by the applicable laws and/or regulations, will not be made publicly available and, if the results of the trial are published, the subject's identity will remain confidential. Subjects will be informed whether private information collected from this research and/or specimens will be used for additional research, even if identifiers are removed.

Subjects will be allowed sufficient time to consider participation in this research trial and have the opportunity to discuss this trial with their family, friends or legally authorized representative, or think about it prior to agreeing to participate.

10.3 Subject Confidentiality

Subjects will be assigned coded subject identification numbers and will not be identified by name. The subject's names and code numbers (code key) will be kept at the site so that subjects can be re-contacted to participate in studies. The study site will maintain the subject's information and code key in locked files or on password protected secured computer servers. Subject confidentiality is strictly held in trust by the site principal investigator and study personnel. This confidentiality is extended to cover testing of biological samples, in addition to the clinical information relating to participating subjects.

No information concerning study data will be released to any unauthorized third party without prior written approval of the Principal Investigator. Research teams who maintain the code key will contact subjects who qualify for future CHIVITT studies. As we are using research immunology assays and not CLIA-certified assays, we will not disclose the results of immunology testing to the participants.

All data and information generated by the clinical site as part of this study (other than a subject's medical records) will be kept confidential by the site principal investigator and other study personnel to the extent permitted by law. This information and data will not be used by the site principal investigator or other study personnel for any purpose other than conducting the study and for potential recruitment into future CHIVITT studies. These restrictions do not apply to: (1) information which becomes publicly available through no fault of the site principal investigator or other study personnel; (2) information which is necessary to disclose in confidence to an IRB solely for the evaluation of the study (3) information which is necessary to disclose to provide appropriate medical care to a study subject; or (4) study results which may be published. Authorized representatives of the Sponsor, university ethics board (IRB), or other auditing agencies may inspect all documents and records required to be maintained by the site principal investigator. This includes, records related to the samples used for this study. The study site will permit access to such records.

To protect privacy, the NIH has provided a Certificate of Confidentiality, CoC. With this CoC, the participating sites cannot be forced to release information that may identify the participant, even by a court subpoena, in any federal, state, or local civil, criminal, administrative, legislative, or other proceedings. The participating sites will use the CoC to resist any demands for information that would identify the participant, except as explained below.

The CoC cannot be used to resist a demand for information from personnel of the United States Government that is used for auditing or evaluation of federally funded projects, like this study or local laws, such as for reporting of communicable diseases.

A CoC does not prevent the participant from voluntarily releasing information about themselves or their involvement in this research. If any person or agency obtains a written consent to receive study information, then the participating sites may not use the CoC to withhold that information.

The CoC does not prevent the participating sites from reporting without the participant's consent, information that would identify the subject as a participant in the study regarding matters that must be legally reported including child and elder abuse, sexual abuse, or wanting to harm themselves or others.

Hotel staff will be providing services as per their standard duties and are instructed to maintain confidentiality as per the standards of the hotel industry. There will be no further control or oversight from the study team over the hotel staff with regards to assurances of confidentiality. Nonetheless, any breaches of confidentiality will be immediately brought to the attention of hotel executives and supervisors to minimize further occurrences.

Electronic data, photo, and video recordings are intended to be collected and stored using secure and password protected means, as described in [Section 2.5.1](#). Participants and the IRB will be informed should there be breaches in confidentiality with these forms of data.

10.4 Data Handling and Record Keeping

The PI is responsible to ensure the accuracy, completeness, legibility, and timeliness of the data reported. Data will be entered into REDCap to record and maintain data for each subject enrolled in this study. For paper source documents, entries should be completed in a neat, legible manner to ensure accurate interpretation of data. Black or blue ink is required to ensure clarity of reproduced copies. When making a change or correction, cross out the original entry with a single line and initial and date the change. Do not erase, overwrite, or use correction fluid or tape on the original.

All data must be reviewed by the clinical team and data entry personnel, who will ensure that they are accurate and complete. All data collection forms and laboratory reports must be reviewed by the clinical team and data entry staff, who will ensure that they are accurate and complete. Adverse events must be graded, assessed for severity and causality, and reviewed by the site principal investigator or designee. Data collection is the responsibility of the clinical trial staff at the site under the supervision of the site principal investigator. During the study, the investigator must maintain complete and accurate documentation for the study.

Study related records, including the regulatory file, study product accountability records, consent forms, subject source documents and electronic records will be maintained indefinitely. No records will be destroyed without the written consent of DMID. Consent forms with specimen retention linked to identifiable specimens will be maintained for as long as the specimens remain in identifiable format.

